## **7.0 Data analysis and statistical considerations**

### **7.1 Sample size determination**

For trauma patients admitted to an ICU, the mean overall nosocomial infection rate is 6 to 18%. (9, 19, 20) The incidence rate of infection could be greater for all surgical ICU patients. Data collected to date indicate that a sustained decrease in BDV of 2.0‰ or more correlates with the onset of infection when the subject is used as his-her control. The average intra subject standard deviation (SD) across time points in 32 mechanically ventilated subjects previously studied was 1.16‰, regardless of the underlying medical conditions. The inter subject SD is expected to be 1.5‰ at most. Using the BDV measurements during the breath sample monitoring period (breath sample assessments every 4 hours), the expected overall SD of the mean BDV measurements (across time points) is less than 1.5‰.

Furthermore, during the monitoring period, the mean difference in the BDV between subjects who are diagnosed with a nosocomial infection and subjects not diagnosed with an infection is expected to be 2.0‰ or more (primary hypothesis). This difference will be considered to be the minimum difference with clinical importance.

Assuming that 5% of the subjects will have a confirmed nosocomial infection over the monitoring period and an overall standard deviation of 1.5‰, a total sample size of 100 subjects (5 infected and 95 non-infected) is required to detect a minimum clinically-important difference of 2.0‰ with at least 80% power at the two-sided 5% significance level.

If the actual rate of nosocomial infections is 10%, then the proposed total sample size of 100 subjects will provide 98% power to detect a mean difference of 2.0‰. Assuming SD to be 1.5‰ (at most) for the change in BDV before and after the diagnosis of an infection is made, a total sample size of 100 subjects and an infection rate of 5%, a mean decrease of 2.0‰ prior to and after the confirmed infection will be detected with 79% power at the one sided 5% significance level (secondary hypothesis).

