If the rate of nosocomial infections is 10%, then the mean decrease of 2.0‰ will be detected with 99% power. The proposed sample size of 100 subjects is sufficient to provide accuracy in estimating the specificity of the BDV analyzer. That is, with a sample size of 100 and assuming that 95% of the subjects will have no confirmed nosocomial infection, the specificity will be estimated with a standard error of less than 5%, and the 95% confidence interval of the estimated specificity will be no greater than 20%.

To account for a missing value rate -- due to study withdrawal (see 5.12 Withdrawal of subjects) or infection failure of up to 10%, the total enrollment target is 110.

***The goal sample size of 100 subjects will be achieved through implementation of the protocol at more than one approved study site.***

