### **7.2 Analysis plan**

Descriptive statistics will be generated. For continuous variables, descriptive statistics may include the number of subjects from whom data was used in the calculation, mean, standard deviation, median, minimum, and maximum; frequencies and percentages may be displayed for categorical data.

A 2-sample t-test will be used to compare the averaged (across time points) BDV between subjects who are diagnosed with an infection, without an infection, with sepsis and without sepsis. A linear mixed effects model with subject specific random effects will be used to compare BDV measurements between infected and non-infected and septic and non-septic subjects. This model will be also used to estimate the intra- and inter-subject variability of the BDV measurements. A paired t-test will be used to compare the BDV measurements prior to and after a diagnosis of infection or sepsis. Fisher's exact test and the Kappa statistic will be used to evaluate the relationship between a positive indication of infection by the BDV and a diagnosis of infection or sepsis in the subsequent 72 hours. Sensitivity, specificity, negative predictive value, positive predictive value and corresponding 95% confidence interval will be calculated.

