## 7. Endpoints and Covariates

We divided the covariates into two categories: the first is related to baseline covariates, such as underlying medical conditions, caloric intake, infection history, immune markers, being on antibiotics, and other concurrent therapies at baseline. Baseline medical conditions will be collected per the Charleston Comorbidity Index. The second category is related to on-study covariates (possibly outcome correlative) like procalcitonin, new antibiotics, new surgeries, new treatments, changes in diet, healing rates, and clinical signs and symptoms (e.g. fever, chills, WBC, breaths per minute, pulse, electrolytes).

While we recognize that some of the aforementioned covariates can affect sample carbon dioxide concentration (ventilator settings, or exogenous oxygen), any diluents will affect both  $^{13}\text{CO}_2$  and  $^{12}\text{CO}_2$  proportionally and will not disturb the  $^{13}\text{CO}_2$ : $^{12}\text{CO}_2$  ratio. Similarly, covariates that compromise air exchange in the lung do not affect the ratio of  $^{13}\text{CO}_2$ : $^{12}\text{CO}_2$  since there is no fractionating process during the exchange process. As long as the patient is producing  $\text{CO}_2$ , there will be exhaled  $\text{CO}_2$  albeit at potentially lower concentrations in subjects with reduced air exchange capacity, but the relative ratio of  $^{13}\text{CO}_2$  to  $^{12}\text{CO}_2$  remains constant. These points being stated, we have modified our study design to collect the necessary covariate data to demonstrate that  $\text{CO}_2$  concentration does not affect the  $^{13}\text{CO}_2$ : $^{12}\text{CO}_2$  ratio, by capturing the following information and the changes to these:

- **Ventilator settings** (Ventilator Mode, Oxygen Concentration, PEEP setting, Tidal Volume/Pressure,  $\text{FiO}_2$   $\text{PaO}_2$  and Flow Rate)
- **Lung dysfunctions** (Baseline comorbidities and diagnosed lung dysfunctions)
- **Nutrition and metabolic status** (Type of Nutrition, Type of Line, and Composition)
- **Comorbidity** (COPD, diabetes, metabolic and lung dysfunction)

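### The before/after paired t-test uses diagnosed subjects only, so it cannot separate an infection effect from a BDV trend over the ICU stay that all subjects share

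*Protocol*

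**What the plan says.** Protocol 7.2 gives one analysis of change around diagnosis: "A paired t-test will be used to compare the BDV measurements prior to and after a diagnosis of infection or sepsis". SAP section 6 and SAP section 9 carry the same sentence.

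Protocol 7.1 attaches the power of the secondary hypothesis to this comparison. The inputs are "Assuming SD to be 1.5‰ (at most) for the change in BDV before and after the diagnosis of an infection is made" and "a mean decrease of 2.0‰ prior to and after the confirmed infection", which "will be detected with 79% power at the one sided 5% significance level" at a 5% infection rate. For the higher rate it adds: "If the rate of nosocomial infections is 10%, then the mean decrease of 2.0‰ will be detected with 99% power". The logic is self-control: Protocol 7.1 says that a sustained fall of 2.0‰ or more "correlates with the onset of infection when the subject is used as his-her control".

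Non-infected subjects enter the two-sample t-test on time-averaged BDV, the mixed model and the diagnostic accuracy estimates. The mixed model is described as a group comparison with subject-specific random effects. No term for study day, for before versus after, or for group by time is stated.

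SAP section 7 lists on-study covariates that include "new antibiotics, new surgeries, new treatments, changes in diet, healing rates". Under Protocol 5.5 every subject, infected or not, is sampled every four hours until general care status, discharge or 28 days.

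**The concern.** Using each subject as his or her own control removes stable differences between subjects. It does not remove changes over time. If BDV tends to fall during an ICU stay for reasons unrelated to infection, the paired test will tend to find a fall in infected subjects even if infection does nothing. If BDV tends to rise, the test will hide a real fall.

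No other planned analysis separates the two. The two-sample t-test averages over time, and the mixed model as written compares levels between groups. Nothing compares the change around diagnosis with the change over the same study days in non-infected subjects, although those subjects supply the same four-hourly series.

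At stake is the reading of the one test powered for the protocol's secondary hypothesis. With a shared trend, its error rate would not be the stated 5%.

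**Working it through.** **Inputs.** From Protocol 7.1: SD of change 1.5‰, mean decrease 2.0‰, one-sided 5%, and "a total sample size of 100 subjects (5 infected and 95 non-infected") at a 5% infection rate, which becomes 10 and 90 at 10%. Drift sizes are assumptions, because the documents give none.

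**Step 1: reproduce the plan's power.** For a paired t-test on n infected subjects, df = n − 1 and the noncentrality is (2.0/1.5) × √n.
- n = 5: noncentrality 2.98, critical t(4) = 2.132, power 78.7% (stated 79%).
- n = 10: noncentrality 4.22, critical t(9) = 1.833, power 98.7% (stated 99%).

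The arithmetic in Protocol 7.1 is right, and it confirms that the powered test uses infected subjects only.

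**Step 2: shared fall, no infection effect.** Replace 2.0 by the drift d, so the noncentrality is (d/1.5) × √n. The chance of a significant result is:

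| Assumed shared fall | n = 5 | n = 10 |
|---|---|---|
| 0 | 5% | 5% |
| 0.25‰ | 9% | 12% |
| 0.5‰ | 15% | 25% |
| 1.0‰ | 34% | 62% |

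For scale, Protocol 7.1 gives an average intra-subject SD of 1.16‰, so each assumed drift is smaller than that. The error grows with the number of infections.

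**Step 3: shared rise with a true infection-related fall of 2.0‰.** The net change is 2.0 − d. With n = 5, a rise of 0.5‰ leaves a net fall of 1.5‰, and power drops from 79% to 58%. A rise of 1.0‰ leaves 34%.

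**Step 4: compare with the change in non-infected subjects over matched days.** With equal SDs and all 95 controls usable, the standard error is 1.5 × √(1/5 + 1/95) = 0.688‰, against 1.5/√5 = 0.671‰ for the paired test. Degrees of freedom rise from 4 to 98. The one-sided test has 89% power, and its type I error under a shared fall of 0.5 or 1.0‰ stays at about 5% in simulation.

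**Step 5: how far that 89% can be relied on.**
- Fewer usable controls, 5 infected, equal SDs: 61% power at 1:1, 75% at 1:2, 80% at 1:3, 83% at 1:4. Break-even with the paired test is about three controls per infected subject.
- Unequal SDs (infected 1.5‰; control SDs assumed), 5 vs 95, no effect, simulated: a pooled-variance test rejects in 13, 19 and 26% of trials at control SDs of 1.0, 0.75 and 0.5‰. Welch's test holds about 5%, with power of about 78%.

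**The case against.** **Drift is assumed.** No section reports a trend common to all subjects. New surgeries, treatments and diet changes happen to individuals at different times. Unless they line up by study day, they add variance rather than a shared shift. SAP section 5 links its roughly 0.5‰ variability to stable nutrition, which is not evidence of drift. This stands: the point is a risk shown over a range. A reader might infer that BDV does drift and that the 5% level is already broken, and the documents do not support that.

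**The reach is limited.** The test serves the protocol's secondary hypothesis in what Protocol 1.0 and 3.0 call a pilot. The SAP's co-primary endpoints are sensitivity and specificity against PCT, and its secondary endpoint concerns BDV variability. A reader might infer that the main conclusions are at risk, but they do not rest on this test. SAP section 6 also sets two-sided 0.05. With 2.5% in the lower tail, the n = 5 figures fall to 4.8, 8.5 and 21.1%. Nor should the table be carried over to the SAP's assumption of equal infected and uninfected numbers, because that would mix one document's split with the other's SD and level.

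**Partly covered elsewhere.** The 72-hour analyses (Fisher's test, kappa, sensitivity, specificity) use non-infected subjects, and a common fall large enough to trigger the BDV rule would appear there as false positives. Protocol 3.0 also foresees covariate models for infection outcome. These are useful, but none of them corrects the before/after test. That the mixed model lacks time terms is inferred from silence.

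**Controls are not free.** From the 89% a reader might infer that using controls raises power. It does so only with equal SDs and nearly all controls usable. Sampling ends on leaving ICU/IMC care, so late index days will have fewer and selected controls. The SAP's own alternative hypothesis is that variability increases after diagnosis, which argues against assuming equal SDs.

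**Conclusion.** The concern holds as a design weakness in one powered secondary test. The paired t-test confounds infection with elapsed time, and no planned analysis removes that, although the control data will be collected. If a shared drift exists, the false-positive rate would be 9 to 34% with 5 infected subjects and 12 to 62% with 10, for falls of 0.25 to 1.0‰. An upward drift of 0.5‰ would take power from 79% to 58% with 5 infected.

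These figures rest on the protocol's SD of change of 1.5‰, its one-sided 5% level, and assumed drift sizes. The protocol's 79% and 99% are themselves correct. The change is justified by the removal of a possible bias, not by a gain in power. It should be made, but the SAP's co-primary endpoints do not depend on it.

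**What to change.** Make the before/after comparison inside the mixed model already planned:

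- Add study day and an infected-by-post-index term, so that the change in infected subjects is compared with the change over the same days in non-infected subjects.
- Define the index day explicitly relative to the diagnosis date, and consistently with Protocol 2.2. That hypothesis concerns a fall before diagnosis, so an index placed at diagnosis would leave an early fall inside the before period.
- Apply each infected subject's index day to non-infected subjects still being sampled on that day.
- Allow unequal variances, through group-specific variances or Welch-type degrees of freedom.
- Keep the paired t-test as a descriptive result.

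**Cost.** No new data are needed, but the index-day scheme has to be written into the SAP before the BDV results are seen. Power with 5 vs 95 is about 78% under unequal-variance inference, close to the paired test's 79%. It reaches 89% only with equal SDs and all controls usable. Even with equal SDs, it falls below 79% with fewer than about three usable controls per infected subject.

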## **6. Analysis Sets/Populations/Subgroups**

The first task is to demonstrate that there is a positive signal associated with the Canary test using the subject as their own control.

A per protocol analysis will be performed following EAC event reconciliation and subsequent database lock. The EAC will determine diagnostic truth by documenting severe sepsis or septic shock events as well as the onset and resolution dates.

Infection documentation will be reviewed by the EAC committee based on best clinical practices, using four categories:

- No suspicion of infection
- Inconclusive evidence of infection
- High suspicion of infection
- Overt infection

For sensitivity and specificity, non-inferiority testing will be performed to rule out a -10% disadvantage according to a one-sided 97.5% lower confidence limit for the BDV – PCT

difference; exact McNemar paired comparison tests will be performed to test BDV non-inferiority relative to PCT. Both endpoints must achieve statistical significance in order to achieve study success.

PPV and NPV will be computed as observed and for a range of possible infection prevalence (10%, 20%, 30%, and 40%). Results will be analyzed in the same manner as sensitivity and specificity.

BDV variations will be assessed using a two-sample t-test to compare the averaged (across time points) BDV between subjects who are diagnosed with a severe sepsis and sepsis shock vs. no severe sepsis or sepsis shock. Also a linear mixed effects model with subject specific random effects will be used to compare BDV measurements between the two diagnostic groups. This model will be also used to estimate the intra- and inter-subject variability of the BDV measurements. A paired t-test will be used to compare the BDV measurements prior to and after a diagnosis of infection or sepsis.

The definition of a positive BDV will be based on a 72-hour window without advance knowledge of the diagnosis. In the absence of clinical details supporting PCT operating characteristics (sensitivity, specificity), two PCT thresholds (0.5 and 2.0) will be evaluated but the 0.5 threshold is deemed to be primary for BDV comparison.

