Descriptive statistics will be generated for patient characteristics, demographics, and on-study events relating to subgroups (see Section 7.4). For continuous variables, descriptive statistics may include the number of subjects from whom data was used in the calculation, mean, standard deviation, median, minimum, and maximum; frequencies and percentages may be displayed for categorical data.

The predicate marker PCT sensitivity is estimated to be between 64-82% based on a recent review of the published literature (19); PCT sensitivity will be assumed to be 75% for sample size calculations. BDV sensitivity is expected to range between 80-90% based on the proof-of-concept study. The study is designed to have at least 80% power and one-sided 2.5% Type I error. A greater than 10% disadvantage for BDV vs PCT (null hypothesis) is to be tested against a less than 10% disadvantage for BDV vs PCT (alternative hypothesis). As shown in Table 1, this non-inferiority hypothesis can be tested with 97 documented infection events. The BDV advantage vs PCT resulting in a -10% one-sided 97.5% lower confidence bound (CB) is also displayed in Table 1; if the sensitivities are 76.5% for BDV vs 75% for PCT based on 97 pairs of infection events, then the one-sided 97.5% lower CB would be -10%, which would establish BDV non-inferiority relative to PCT.

Table 1: One-sided 97.5% Lower 97.5% Confidence Limit: Sensitivity Paired Differences (simulation)

	Power	N-I
Confidence level, 1-<math>\alpha</math> (one-sided)	0.975	0.975
Expected difference, <math>\pi_T - \pi_S, \Delta_1</math>	0.100	0.015
Proportion discordant, <math>\eta = \pi_{10} + \pi_{01}</math>	0.400	0.315
Proportion both yes, <math>\pi_{11}</math>	0.600	0.600
Lower limit for <math>\pi_T - \pi_S, LL</math>	-0.100	-0.100
Number of simulations	1000	1000
Random seed for simulations	123	123

Power (%)	89	51
n (number of pairs)	97	97

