The predicate marker PCT specificity is estimated to be between 56-78% based on a recent review of the published literature (19); PCT specificity will be assumed to be 65% for sample size calculations. BDV specificity is expected to range between 70-80% based on the proof-of-concept study. The study is designed to have at least 80% power and one-sided 2.5% Type I error. A greater than 10% disadvantage for BDV vs PCT (null hypothesis) is to be tested against a less than 10% disadvantage for BDV vs PCT (alternative hypothesis). As shown in Table 2, this non-inferiority hypothesis can also be tested with 97 documented non-infection events. The BDV advantage vs PCT resulting in a -10% one-sided 97.5% lower confidence bound (CB) is also displayed in Table 2; if the specificities are 66.5% for BDV vs 65% for PCT based on 97 pairs of non-infection events, then the one-sided 97.5% lower CB would be -10%, which would establish BDV non-inferiority relative to PCT. A 10% non-inferiority delta with respect to both sensitivity and specificity ensures that the performance of BDV is comparable to PCT, considering the difference in sampling methods and the potentially greater convenience of breath sampling for BDV.

Table 2: One-sided 97.5% Lower Confidence Limit: Specificity Paired Differences simulation)

	Power	N-I
Confidence level, 1-<math>\alpha</math> (one-sided)	0.975	0.975
Expected difference, <math>\pi_T - \pi_S, \Delta_1</math>	0.100	0.015
Proportion discordant, <math>\eta = \pi_{10} + \pi_{01}</math>	0.400	0.315
Proportion both yes, <math>\pi_{11}</math>	0.100	0.100
Lower limit for <math>\pi_T - \pi_S, LL</math>	-0.100	-0.100
Number of simulations	1000	1000
Random seed for simulations	123	123
Power (%)	87	52
n (number of pairs)	97	97

We will also categorize infections per respiratory and non-respiratory infections within our data analysis to determine if there is an impact on the breath delta value.

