## 9. Statistical Methodology

Descriptive statistics will be generated. For continuous variables, descriptive statistics may include the number of subjects from whom data was used in the calculation, mean, standard deviation, median, minimum, and maximum; frequencies and percentages may be displayed for categorical data.

A 2-sample t-test will be used to compare the averaged (across time points) BDV between subjects who are diagnosed with an infection, without an infection, with sepsis and without sepsis. A linear mixed effects model with subject specific random effects will be used to compare BDV measurements between infected and non-infected and septic and non-septic subjects. This model will be also used to estimate the intra- and inter-subject variability of the BDV measurements. A paired t-test will be used to compare the BDV measurements prior to and after a diagnosis of infection or sepsis. Fisher's exact test and the Kappa statistic will be used to evaluate the relationship between a positive indication of infection by the BDV and a diagnosis of infection or sepsis in the subsequent 72 hours. Sensitivity, specificity, negative predictive value, positive predictive value and corresponding 95% confidence interval will be calculated.

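### The SAP counts its co-primary BDV–PCT pairs as events and tests them as independent, with no limit of one pair per subject and no allowance for within-subject correlation

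*Protocol*

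**What the plan says.** **Co-primary comparison (SAP section 6).** For sensitivity and for specificity, "non-inferiority testing will be performed to rule out a -10% disadvantage according to a one-sided 97.5% lower confidence limit", and "exact McNemar paired comparison tests will be performed to test BDV non-inferiority relative to PCT". Both endpoints must succeed. The design statement is "The study is designed to have at least 80% power and one-sided 2.5% Type I error".

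The counting unit in the sample-size text is the event. For sensitivity, "this non-inferiority hypothesis can be tested with 97 documented infection events", and the worked example refers to "75% for PCT based on 97 pairs of infection events". For specificity, "this non-inferiority hypothesis can also be tested with 97 documented non-infection events". Neither document defines a non-infection event. The same section has the endpoint committee document severe sepsis or septic shock events with onset and resolution dates, so one subject can have more than one. There is no rule for repeat events and no clustered method.

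**Association analysis (Protocol 7.2, repeated in SAP section 9).** "Fisher's exact test and the Kappa statistic will be used to evaluate the relationship between a positive indication of infection by the BDV". The outcome on the other side of the table is "a diagnosis of infection or sepsis in the subsequent 72 hours". Sensitivity, specificity, PPV and NPV with 95% intervals follow. Neither section says whether a row of the 2×2 table is a subject, a window, an event or a reading. Subject random effects are specified, but only for the continuous BDV values.

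**The concern.** A McNemar test, like the power in SAP Tables 1 and 2, treats each pair as a separate piece of information. Two pairs from one patient share physiology, treatment and comorbidity, so the BDV-minus-PCT difference is likely to be positively correlated within a patient. If such pairs are counted as independent, the standard error is too small, the lower confidence limit sits too high, and the 2.5% error is exceeded.

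This matters most for the co-primaries, because they decide study success. If the unit is chosen after the data are seen, that choice can also move the result across the margin. The same mechanism would affect Fisher's test, kappa and the accuracy intervals if several windows or readings per subject entered the table.

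**Working it through.** **1. Reproduce the SAP's power with independent pairs.** Inputs from SAP Tables 1 and 2: n = 97, difference d = 0.10, discordance η = 0.40, margin 0.10, one-sided 2.5%.

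Power = Φ[(d + 0.10)/SE − 1.96], with SE = √((η − d²)/n).

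- Power column: SE = √(0.39/97) = 0.0634; 0.20/0.0634 = 3.154; Φ(1.194) = 88.4%. Stated: 89% and 87%.
- N-I column (d = 0.015, η = 0.315): SE = 0.0570; 0.115/0.0570 = 2.019; Φ(0.059) = 52.3%. Stated: 51% and 52%.
- Lower limit at d = 0.015: 0.015 − 1.96 × 0.0570 = −9.7%. Stated: −10%.

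The tables therefore reproduce with 97 independent pairs and no clustering allowance. Simulation with Wald, Tango and Newcombe limits gives 88% for the power columns.

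**2. How many events per subject would be needed?** Protocol 3.0 enrols up to 100 subjects and Protocol 7.1 sets an enrolment target of 110. SAP section 5 takes a 50% infection rate. The SAP states no total enrolment.

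- 100 × 0.50 = 50 infected; 97/50 = 1.94 events each.
- 110 × 0.50 = 55 infected; 97/55 = 1.76 events each.
- One pair per subject on both endpoints would need 97 + 97 = 194 subjects, a number that neither document states.

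At the Protocol 7.1 infection rates of 5% and 10%, 100 subjects give 5 or 10 infected, so 97 events is not a realistic target.

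**3. Effect of clustering.** The documents give neither the pairs per subject (m) nor the within-subject correlation (ICC); both are assumptions here. Design effect DEFF = 1 + (m − 1) × ICC. True one-sided error = 1 − Φ(1.96/√DEFF). Power uses SE × √DEFF.

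| Pairs per subject | ICC | DEFF | One-sided error | Power |
|---|---|---|---|---|
| 1 | any | 1.00 | 2.5% | 88% |
| 2 | 0.3 | 1.30 | 4.3% | 79% |
| 2 | 0.5 | 1.50 | 5.5% | 73% |
| 3 | 0.5 | 2.00 | 8.3% | 61% |

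Few repeats: if 16 of 81 subjects have two events and 65 have one, that is 32 + 65 = 97 pairs. With unequal cluster sizes, m in the formula becomes Σm²/Σm = (64 + 65)/97 = 1.33. DEFF is then 1.10 (ICC 0.3) or 1.165 (ICC 0.5), and the error 3.1% or 3.5%. Simulation of this case gave 3.1% to 3.6%.

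**4. Fisher's test.** Simulated with 100 subjects, non-overlapping 72-hour windows, and assumed rates per window of 20% BDV-positive and 10% infected, at nominal two-sided 5%. Twenty-eight days hold at most 28 × 24/72 = 9.3, so 9 full windows.

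| Windows per subject | ICC (BDV and infection) | Rejection rate under the null |
|---|---|---|
| 1 | – | 2.5% |
| 2 | 0.3 | 4.6% |
| 5 | 0.3 | 7.2% |
| 9 | 0.3 | 11.6% |
| 9 | 0.5 | 24% |
| 9 | 0.5 for BDV, 0 for infection | 4.2% |

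Substantial inflation needs many windows per subject and clustering of both BDV positivity and infection.

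**The case against.** The strongest reply is that the subject is the natural unit almost everywhere else. Protocol 7.1 sizes the study on 5 infected and 95 non-infected subjects and bases specificity on subjects. Protocol 10.1 records an infection status for the subject. SAP section 5 says its sample size rests on equal proportions of infected and uninfected subjects, which matches the equal 97 and 97. On that reading the word event is loose drafting and there is no inflation. This is a fair reading and it sets the lower end of the range, but it is not written as a rule. It also needs about 194 subjects, which the documents do not provide for.

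A second reply is that the two-each case assumes every infected subject contributes two pairs. That stands: with few repeats the error stays near 3 to 3.6%.

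A third reply is that Fisher's test and kappa do not carry the Protocol's primary hypothesis, which is a mean BDV difference. Protocol 3.0 also describes a pilot that will work out how to control false positives from repeated opportunities to test positive. That lowers the weight of the association analysis. It does not touch the SAP co-primaries.

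A reader might go further and infer that the plan pools the 4-hourly readings, so that Fisher p-values are far too small. No section says so. Simulated error rates of 29 to 47% under such pooling depend on assumed prevalence and persistence of BDV status as well as on the pooling itself. A reader might also infer that no subject-level table can be built, because a never-positive subject has no start for the 72 hours. It can be built: never positive and uninfected is a true negative; never positive and infected is a false negative. The unclear case is a positive BDV with infection outside the 72 hours.

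**Conclusion.** The point holds for the SAP co-primaries. Pairs are counted as events, the method and power assume independence, and nothing restricts or adjusts for repeat pairs. Depending on inputs that the documents do not give, the one-sided error is 2.5% (one pair per subject), about 3 to 3.6% (few repeats) or about 4.3 to 5.5% (two each, ICC 0.3 to 0.5). In the last case power is 73 to 79%, below the 80% target. Two each is roughly what 97 infection events requires at 100 to 110 subjects and a 50% infection rate.

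For Fisher, kappa, sensitivity, specificity, PPV and NPV, the finding is an unstated unit of analysis. The documents do not support the claim that these results will be anti-conservative; that follows only if repeated windows or readings from one subject are pooled.

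**What to change.** **SAP section 6.** Choose one of these before unblinding:

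- Each subject contributes one pre-specified BDV–PCT pair: the first adjudicated event for a subject who progresses, and one pre-specified window for a subject who does not.
- Keep event-level pairs, define a non-infection event, and use a subject-clustered paired comparison: a clustered McNemar test, GEE with robust variance, or a subject-level bootstrap. The bootstrap is suitable only with enough infected subjects; about 5, as in Protocol 7.1, is too few.

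In either case, restate the power in Tables 1 and 2 for the number of independent subjects, and state the total enrolment that this implies.

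**Protocol 7.2 and SAP section 9.** Build the Fisher and kappa table, and the accuracy measures, with one row per subject. State how a positive BDV with infection outside 72 hours is classified. Fixed 72-hour blocks are not a good substitute, because a positive late in one block can be separated from a diagnosis early in the next.

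**Cost.** A few sentences of SAP text and modest programming, somewhat wider confidence limits, and a less favourable stated power. With one pair per subject and 50 infected subjects, for example, SE = √(0.39/50) = 0.0883, 0.20/0.0883 = 2.265, and power is Φ(0.305) = 62%. By the same formula, 80% power needs 77 independent pairs per endpoint.
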